#### **10.6.1.3.2 Infusion-associated reactions**

Some AEs may be manifestations of IARs, including hypersensitivity reaction, acute phase reactions (APR), and cytokine release syndrome (CRS), as described in [Section 10.6.1.3.2.1](#), [Section 10.6.1.3.2.2](#), and [Section 10.6.1.3.2.3](#), respectively. However, original signs and symptoms must be reported as AEs. In the e-CRF, investigators are asked to identify whether a specific AE represents a clinical manifestation of the IAR.

Infusion-associated reactions are defined as AEs that occur during the infusion or within up to 24 hours after the start of infusion and are considered as related or possibly related to the study treatment by the investigator or the sponsor. An event occurring  $\geq 24$  hours after the start of an infusion may be judged an IAR at the discretion of the investigator or sponsor. For this study of olipudase alfa, IARs may present as different types of reactions, such as hypersensitivity reactions, APRs, and CRS.

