#### **11.4.2.1 Adverse events**

The definitions in [Section 10.6.1](#) will be used for AEs. Pre-treatment AEs will be listed and presented separately from treatment-emergent AEs.

Adverse events will be coded according to the most recent version of the Medical Dictionary for Regulatory Activities (MedDRA). Adverse event incidence tables will be presented by MedDRA system organ class (SOC) (sorted by internationally agreed order) and preferred term (PT) sorted in decreasing number of patients within SOCs and further alphabetical order within the same number of patients over different PTs for each age group, the number (n) and percentage (%) of patients experiencing an AE. Multiple occurrences of the same event in the same patient will be counted only once in the tables within a treatment period. The denominator for computation of percentages is the safety population for the entire study and each age group cohort.

Adverse events will be classified into pre-defined standard categories according to chronological criteria:

- Pre-treatment AEs: AEs that occurred or worsened during the pre-treatment period;
- Treatment-emergent AEs (TEAEs): AEs that occurred or worsened during the on-treatment period);
- Post-treatment AEs: AEs that occurred or worsened during the post-treatment period.

If the start date of an AE is incomplete or missing, then the AE will be considered as a TEAE unless a partial date shows it as a pre- or post-treatment event.

All AEs reported in the study will be listed, sorted by patient, and onset date.

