1.5 MODIFICATIONS FROM THE STATISTICAL SECTION OF THE PROTOCOL

In the section of statistical considerations of the protocol, the baseline for white blood cell count, platelet count, and hemoglobin was defined as the mean of 2 samples collected greater than 24 hours apart during the screening period. The baseline definition is modified in the SAP as the average of all measurements taken before the first infusion.

The statistical considerations of the protocol mentions that Infusion Associated Reactions (IAR), Acute phase reaction (APR) and cytokine release syndrome (CRS) will be listed as part of adverse events of special interest (AESI). However, per protocol, AESIs are reported as original signs and symptoms and only IARs were specifically identified in the eCRF. Consequently, APR and CRS cannot specifically be listed, but the details of these AESIs will be provided in patient narratives, and discussed in the clinical study report (CSR) as necessary.

In the section of statistical considerations of the protocol, the post-treatment period was defined as the time after the EOS visit. However, no data are expected to be collected after the EOS visit. Therefore, the post-treatment period has been removed from this SAP.

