2.6.1 Adverse events

2.6.1.1 Definitions

AEs are defined in protocol Section 10.6.1. AEs will be coded according to the version of Medical Dictionary for Regulatory Activities (MedDRA) in use at the time of database lock. Adverse event summaries will include the number of events (N), number (n) and percentage (%) of patients experiencing an adverse event. The denominator for computation of percentages is the safety population for the entire study and for each age group cohort. Sorting order will follow the

internationally agreed MedDRA system organ class (SOC) order, then by decreasing number of patients overall in preferred terms (PTs) within SOCs, and further alphabetically within the same number of patients over different PTs. When more than one PT has same number of events within the same SOC, the order of presentation will be alphabetical in PTs.

The AEs will be classified into different periods of occurrence as follows:

- Pre-treatment adverse events: AEs that started before the start of the first infusion.
- TEAEs: AEs that started during the on-treatment period.

If an AE date/time of onset is incomplete, an imputation algorithm will be used to classify the adverse event within the appropriate adverse event period. The algorithm for imputing date/time of onset will be conservative and will classify an adverse event as treatment emergent unless there is definitive information to determine otherwise. Details on classification of AEs with missing or partial onset dates are provided in [Section 2.11.2](#). If an AE worsens in severity, only the worst severity is captured on the AE log page in the e-CRF.

The AE log page in the e-CRF captures the date when the event became serious. If and when this date is non-missing, it indicates that the AE started as non-serious and became serious after few days. To account for non-serious and serious parts of the AE collected in one AE log page, this AE will be split into two AEs – one non-serious, and one serious AE – with the same AE number, with the following modifications in data for these two AEs:

- Non-serious AE: AE end date, AE outcome, date of death or hospitalization, autopsy information, criterion for serious adverse event (SAE) will be blank.
- Serious AE: AE start date will use the date the event became serious.

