The following are AEs of special interest:

Protocol-defined IAR: Any AE that is considered related or possibly related to study treatment as judged by the investigator or the sponsor is defined as a protocol-defined IAR. Sponsor identification will reconcile with investigator identification of IAR before the database lock.

The following summaries will be produced by primary SOC and PT, by age group cohorts and overall:

- Protocol-defined IARs.
- Protocol-defined IARs by the worst severity.
- Protocol-defined IARs started during infusion.
- Protocol-defined IARs started between 0 hours (exclusive) and 3 hours (exclusive) post end of infusion.
- Protocol-defined IARs started between 3 hours (inclusive) and 24 hours (inclusive) post end of infusion.
- Protocol-defined IARs started between 24 hours (exclusive) and 72 hours (inclusive) post end of infusion.
- Protocol-defined IARs started after 72 hours post end of infusion.

Algorithm-defined IAR: All AEs that start between the start of infusion and the end of infusion plus 24 hours are defined as algorithm-defined IARs, irrespective of the perceived relation with study treatment.

The following summaries will be produced by primary SOC and PT, by age group cohorts and overall:

- Algorithm-defined IARs (including any TEAEs with missing time but happened on the same day or the day after the infusion)

A subset of protocol-defined IARs will also be defined programmatically by searching for preferred terms within Hypersensitivity SMQs (identified using SMQ code 20000214 Broad and Narrow scope). The summaries of Hypersensitivity IARs will be provided by primary SOC and PT.

Pregnancy: Pregnancy of a female patient entered in the study as well as pregnancy occurring in female partner of a male patient enrolled in this study is captured as an adverse event. In addition, e-CRF provides urine pregnancy test results as positive or negative. Labs provide serum pregnancy test results. Pregnancies will be provided in the overview of AE summary and the pregnancy test results will be provided as part of patient narrative.

Symptomatic overdose: This is captured as an adverse event in this study. For details, please see Section 10.6.4.1 in the protocol. The symptomatic overdose data will be provided as part of patient narrative.

Asymptomatic overdose: This is captured as an adverse event with verbatim term as 'Asymptomatic overdose'. Asymptomatic overdose data will be provided as part of patient narrative.

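### SAP 2.6.1.3 defines a protocol-defined IAR by relatedness alone, omitting the protocol's 24-hour onset condition and its judgment step for later events, and SAP 1.5 does not declare the difference

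*SAP*

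**What the plan says.** **Protocol definition.** Protocol 10.6.1.3.2 sets the onset condition: "Infusion-associated reactions are defined as AEs that occur during the infusion or within up to 24 hours after the start of infusion". It joins this with 'and' to a rating of related or possibly related by the investigator or the sponsor. An event 24 hours or more after the start of infusion "may be judged an IAR at the discretion of the investigator or sponsor". In the e-CRF, "investigators are asked to identify whether a specific AE represents a clinical manifestation of the IAR".

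**SAP definition.** SAP 2.6.1.3 says that every adverse event "considered related or possibly related to study treatment as judged by the investigator or the sponsor is defined as a protocol-defined IAR". It gives no onset condition and no rule for later events. The next sentence reads: "Sponsor identification will reconcile with investigator identification of IAR before the database lock".

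**Links between the two.** Protocol 11.4.2.1 says that the definitions in its Section 10.6.1 "will be used for AEs. Pre-treatment AEs will be listed and presented separately" from treatment-emergent ones. SAP 2.6.1.1 likewise states: "AEs are defined in protocol Section 10.6.1".

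**Declared changes.** SAP 1.5 lists three departures from the protocol's statistical section: the baseline for three hematology parameters, the separate listing of acute phase reactions and cytokine release syndrome, and removal of the post-treatment period. Under the second it notes that, per protocol, "AESIs are reported as original signs and symptoms and only IARs were specifically identified in the eCRF". None of the three changes the IAR definition.

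**The concern.** IARs are a named component of the primary safety endpoint (Protocol 9.1). A table headed protocol-defined IAR tells its reader that the protocol's definition was applied. On the SAP's wording it was not, because relatedness admits an event at any onset without the separate judgment that the protocol requires for later events.

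Three outputs depend on this set: the IAR tables by severity and onset, the hypersensitivity subset (SAP 2.6.1.3) and a narrative criterion (SAP 2.10). There is also a reproducibility problem. One programmer could select on the causality field and another on the e-CRF identification of IARs. Both could claim to follow the SAP, and they could obtain different sets.

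**Working it through.** There is no figure in the plan to reproduce. The check is a comparison of the rules by type of event, followed by one clock conversion.

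**Step 1. Which events enter under each rule**

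| Event | Protocol 10.6.1.3.2 | SAP 2.6.1.3 as written | If the e-CRF/reconciled identification is used |
|---|---|---|---|
| Related, onset within 24 h of infusion start | IAR | IAR | IAR if identified |
| Related, later onset, judged an IAR | IAR | IAR | IAR |
| Related, later onset, not judged an IAR | Not an IAR | IAR | Not an IAR |
| Later onset, judged an IAR, not rated related | Open: the late-event sentence does not repeat relatedness | Not an IAR | IAR |
| Causality missing | Not by the 24 h rule; later events only if judged | IAR in summary tables, through SAP 2.11.2 | IAR if identified |

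The third and fifth rows give the excess under the SAP wording. The fourth row is a possible shortfall. For the fifth row, SAP 2.11.2 limits the substitution to summary tables, so its effect on narrative selection is less clear. Protocol 10.6.1.4.2 requires a relationship for every AE, so such records should be few.

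**Step 2. Whether another readable summary gives the protocol set**

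- *Algorithm-defined IAR (SAP 2.6.1.3).* It has an onset window but ignores relatedness, and its window ends 24 hours after the end of infusion.
- *Onset bins for protocol-defined IARs (SAP 2.6.1.3).* The post-infusion bins are also timed from the end of infusion. Infusions last about d = 20 minutes to 4.5 hours (Protocol 8.3.2). A bin that closes 24 h after the end therefore closes 24 + d after the start: 24 + 0.33 = 24.33 h to 24 + 4.5 = 28.5 h. The protocol's cut-off falls inside the bin that runs from 3 to 24 h after the end, at 24 − d: 24 − 0.33 = 23.67 h to 24 − 4.5 = 19.5 h. No bin separates late events that were judged IARs from those that were not.
- *Potentially related TEAEs (SAP 2.6.1.2).* This set uses the investigator's rating only. Among treatment-emergent events, the literal IAR set is this set plus AEs that only the sponsor rated related.

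No readable summary reproduces the protocol set. SAP 2.6.1.9 is redacted and cannot be checked.

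**Step 3. Whether the difference is declared**

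SAP 1.5 does not mention it. The readable items of SAP 1.6 do not either; its two redacted items concern changes from the previous SAP version, not from the protocol.

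**Step 4. Size**

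The excess is the number of AEs in the third and fifth rows. The documents give no count or rate for either.

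**The case against.** The strongest reply is that the e-CRF identification is what is meant. The sentence after the definition reconciles identification of IARs, not of relatedness, and that step would be pointless if relatedness alone settled the matter. SAP 1.5 says that IARs were identified in the e-CRF, and the label itself points to the protocol. This is plausible as to intent. It does not cure the text: causality and IAR identification are separate judgments, the definition names only the first, and the reconciliation sentence neither states a criterion nor narrows the definition.

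The second reply concerns size, and it largely stands. Protocol 4.1 reports that related AEs in the adult Phase 1b study were predominantly IARs, and Protocol 6.4 places related AEs in that study generally 12 to 48 hours post-dose. Together these suggest that late related events were mostly classed as IARs. Protocol 10.6.1.3.2.2 treats acute phase reactions, typically seen 12 to 72 hours after infusion, as a type of IAR. Close agreement between the IAR and related-TEAE tables would therefore be unsurprising under the protocol definition too, and is not evidence of error.

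Third, SAP 1.5 covers the protocol's statistical section, and the IAR definition lies outside it. This is a weak reply, because Protocol 11.4.2.1 brings the Section 10.6.1 definitions into that section.

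Fourth, over-inclusion in narratives is conservative, and no test uses the IAR count. Both are true, and they limit the severity.

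**Conclusion.** The point holds as a defect of definition and labelling. The SAP's rule for protocol-defined IARs is broader than the protocol's for late related events and for AEs with missing causality. It may be narrower for late events judged IARs without a related rating. The departure is undeclared, and no readable summary restores the protocol set.

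A reader might infer that the reported IAR rate will be materially inflated. The documents do not support that. The excess is unknown and is zero if every late related AE is judged an IAR and no causality rating is missing. Late typical onset does not show misclassification either, since the protocol allows late events to be IARs. For the same reason the SAP's bin for events more than 72 hours after infusion is not itself contrary to the protocol, and a strict 24-hour limit would not be the protocol definition. Nor do the documents show a deliberate redefinition; imprecise drafting is an equally good explanation.

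Severity is minor to moderate: the analysis is single-arm and descriptive, but the affected rate belongs to the primary safety endpoint. The conclusion rests on reading the SAP definition as written and on the readable sections only.

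**What to change.** Define protocol-defined IAR in SAP 2.6.1.3 as either:

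- (a) an AE rated related or possibly related by the investigator or the sponsor, with onset during the infusion or within 24 hours after infusion start; or
- (b) an AE with later onset that the investigator identified as an IAR in the e-CRF, or that the sponsor identified as one in the pre-lock reconciliation.

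Show (b) in its own row. The sponsor should state whether (b) also requires relatedness, because the protocol's late-event sentence does not repeat it. Name the e-CRF variable, and say how AEs with missing causality are handled for this set. Base the hypersensitivity subset and the narrative criterion on the same set. The algorithm-defined IAR can stay as a separately named definition.

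If the broader set is intended, rename it, for example 'related AEs, investigator or sponsor', and declare it in SAP 1.5.

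The cost is SAP wording and a few lines of programming. Onset relative to infusion is already needed for the bins, and the e-CRF identification and reconciliation are already planned. The reported IAR count may change slightly: it falls if unjudged late events leave, and rises if judged late events without a related rating enter.

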2.6.1.4 Adverse events of other interest

Infections: TEAEs of infections are defined under the system organ class of Infections and Infestations. These TEAEs will be included in the summary of all TEAEs by primary SOC and PT.

Bleeding: TEAEs of bleeding are defined under the standard MedDRA queries (SMQs) of Hemorrhages (identified using SMQ code 20000038 Broad and Narrow scope). Bleeding AE data will be summarized by SOC and PT for each age cohort and overall.

2.6.1.5 Serious adverse events

The following summaries will be provided by primary SOC and PT, by age group cohorts and overall:

- Treatment-emergent serious adverse events.

2.6.1.6 Adverse events leading to permanent treatment discontinuation

In this study, if the treatment is discontinued permanently, the patient is withdrawn from the study. A temporary dose interruption is not considered permanent discontinuation of study treatment. AEs leading to permanent treatment discontinuation will be provided as part of the patient narrative.

2.6.1.7 Deaths

Death is reported as a fatal outcome on the AE log page in the e-CRF. All deaths reported in the trial will be provided as part of the patient narrative.

2.6.1.8 Potential Quantifiable Dose Limiting Toxicities

Potential quantifiable Dose Limiting Toxicities will be provided in a by patient data listing.

2.6.1.9 [REDACTED]

- [REDACTED]
- [REDACTED]
- [REDACTED]
- [REDACTED]
- [REDACTED]
- [REDACTED]

2.6.2 Physical examinations

Complete physical examinations data will be collected at screening, Day 1/Week 0, Week 12, 26, 38 and 52 (or at withdrawal if withdrawn prematurely and not done within 12 weeks prior to withdrawal). These examinations will include the evaluation of normal versus abnormal in following body systems: general appearance, examination of the skin; head, eyes, ears, nose, and throat; lymph nodes; heart, lungs, and abdomen; extremities and joints. Complete physical examination (except overall neurological exam) will be classified as normal or abnormal. Frequency shift tables will be provided.

An abbreviated physical examination will assess only the general appearance with evaluation of normal versus abnormal of the patient and is only required prior to each infusion when a complete exam is not indicated. A listing of the abbreviated physical examination data will be provided.

Tanner stage for physical gender-related development will be assessed at Screening, Week 12, Week 26, Week 38 and Week 52 (or at withdrawal if withdrawn prematurely and not done within 12 weeks prior to withdrawal). A data listing will be provided.

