## 7 SELECTION OF PATIENTS

### 7.1 INCLUSION CRITERIA

To enter this study, patients must fulfill the following criteria:

- I 01. The patient and/or patient's parent(s)/legal guardian(s) must provide written informed assent/consent prior to any protocol-related procedures being performed.
- I 02. The patient is male or female <18 years of age on the date of signed informed assent/consent.
- I 03. The patient has documented deficiency of ASM consistent with NPD, as measured in peripheral leukocytes, cultured fibroblasts, and/or lymphocytes.
- I 04. The patient has a spleen volume  $\geq 5$  multiples of normal (MN) measured by magnetic resonance imaging (MRI); patients who have had partial splenectomies will be allowed if the procedure was performed  $\geq 1$  year before screening and the residual spleen volume is  $\geq 5$  MN.
- I 05. The patient's height is -1 Z-score or lower.
- I 06. Female patients of childbearing potential must have a negative serum pregnancy test for beta-human chorionic gonadotropin ( $\beta$ -hCG).
- I 07. Female patients of childbearing potential and male patients are required to practice true abstinence in line with their preferred and usual lifestyle or use two acceptable effective methods of contraception, a barrier method such as a condom or occlusive cap (diaphragm or cervical/vault cap) with spermicidal foam/gel/film/cream/suppository and an established non-barrier method such as oral, injected, or implanted hormonal methods, an intrauterine device or intrauterine system for the duration of the study.

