## 9 ASSESSMENT OF INVESTIGATIONAL MEDICINAL PRODUCT

### 9.1 PRIMARY ENDPOINT - SAFETY

Primary safety endpoints include data pertaining to the safety and tolerability of olipudase alfa: assessment of AEs/TEAEs, including IARs; physical examinations; neurological examinations; clinical laboratory evaluations; vital sign measurements; ECGs; safety biomarkers; Doppler echocardiography and liver ultrasound Doppler; and immune response assessments.

A site physician will assess safety findings as normal, abnormal but not clinically significant (NCS), or abnormal and clinically significant (CS). Any abnormal findings that meet the definition of an AE per [Section 10.6](#) will be recorded on the AE e-CRF.

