#### **11.4.2.5 Physical examinations and neurological examinations**

The frequencies and percent of patients with normal/abnormal findings at baseline and successive visits will be summarized.

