2.6.3 Neurological examinations

Neurological examinations assessments will be collected at screening, Day 1/Week 0, Week 12, 26, 38, and 52 (or at withdrawal if withdrawn prematurely). They will include, but are not limited to the patient's mental status, posture, cranial nerves, motor system including muscle atrophy, tone and power, reflexes, sensory system, coordination, gait, and age-appropriate responses.

Neurological examinations will be classified as normal/abnormal findings. Frequency shift table will be provided.

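### Physical and neurological examinations are graded on three levels under the protocol but tabulated on two, so a body system abnormal at baseline cannot show worsening in the shift tables

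*SAP*

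**What the plan says.** Protocol 9.1 opens "Primary safety endpoints include data pertaining to the safety and tolerability of olipudase alfa" and names physical and neurological examinations among the components. It then sets the grading: "A site physician will assess safety findings as normal, abnormal but not clinically significant (NCS), or abnormal and clinically significant (CS"). Abnormal findings that meet the adverse event definition also go on the adverse event form.

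The analysis text uses two levels in both documents:

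- Protocol 11.4.2.5: "The frequencies and percent of patients with normal/abnormal findings at baseline and successive visits will be summarized".
- SAP 2.6.2, on collection: "These examinations will include the evaluation of normal versus abnormal in following body systems". The list that follows includes the abdomen. On analysis: "Complete physical examination (except overall neurological exam) will be classified as normal or abnormal. Frequency shift tables will be provided".
- SAP 2.6.3: "Neurological examinations will be classified as normal/abnormal findings. Frequency shift table will be provided".

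SAP 1.5, which lists changes from the protocol's statistical section, does not mention examinations.

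On the state of the abdomen at entry, inclusion criterion I 04 in Protocol 7.1 reads "The patient has a spleen volume" of at least 5 "multiples of normal (MN) measured by magnetic resonance imaging (MRI"). It is an imaging criterion. Neither document states what grade the abdominal examination will have at baseline.

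**The concern.** A shift table exists to show movement from baseline in both directions. With two levels, abnormal is already the worst category, so a system that starts abnormal can register only stability or improvement. The step from NCS to CS, which the protocol's own scale was built to separate, disappears before tabulation.

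Three consequences follow.

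- **Abdomen.** In this disease it is the region most likely to be abnormal at entry, so its table would be nearly one-directional.
- **Unit of classification.** SAP 2.6.2 does not say whether the shift is tabulated by body system or for the complete examination as a whole. If it is the whole, one abnormal abdomen puts the patient in the abnormal row, and a new skin, heart, lung or joint finding cannot show as a shift.
- **Neurological examination.** Exclusion criteria E 03 (acute or rapidly progressive neurological abnormalities) and E 05 (delayed gross motor skills) make a normal baseline likely for most patients. New abnormality can then be shown, but a minor new finding and a clinically significant one fall in the same cell.

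**Working it through.** The plan gives no figure to reproduce here: there is no sample size calculation and no test on the examinations. The check counts table cells and then asks how much the third level recovers.

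**Step 1: cells available from each baseline grade.**

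| Scale | Baseline | Better | Same | Worse |
|---|---|---|---|---|
| Two levels (Protocol 11.4.2.5, SAP) | normal | 0 | 1 | 1 |
| | abnormal | 1 | 1 | 0 |
| Three levels (Protocol 9.1) | normal | 0 | 1 | 2 |
| | NCS | 1 | 1 | 1 |
| | CS | 2 | 1 | 0 |

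The third level adds a worsening cell for patients who start at NCS. It adds none for patients who start at CS.

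**Step 2: how likely is an abnormal abdomen at baseline?** By the formula in SAP 2.8.1, spleen volume in multiples of normal is the volume in cm³ divided by (2 × weight in kg). A value of 5 is therefore 5 × 2 = 10 cm³/kg, against 2 cm³/kg at 1 multiple of normal. Protocol 4.1 calls hepatosplenomegaly the most common manifestation. An abnormal abdomen in nearly every patient is a strong inference, but remains an inference. Taking the planned minimum of 20 patients:

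- 100% abnormal: 20 × (1 − 1.00) = 0 patients can show worsening in the two-level table.
- 95% abnormal (assumed): 20 × (1 − 0.95) = 1 patient.
- 90% abnormal (assumed): 20 × (1 − 0.90) = 2 patients.

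**Step 3: what the three-level table could show.** Let all 20 be abnormal at baseline and let a share s be graded CS. Then m = 20 × (1 − s) patients have a worsening cell. If each moves from NCS to CS independently with probability p, the chance that the table shows at least one such shift is 1 − (1 − p)^m. Neither s nor p is in the documents; both are varied as assumptions.

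| s (CS at baseline) | m | p = 10% | p = 15% | p = 20% | Two-level table |
|---|---|---|---|---|---|
| 0% | 20 | 0.878 | 0.961 | 0.988 | 0 |
| 50% | 10 | 0.651 | 0.803 | 0.893 | 0 |
| 100% | 0 | 0 | 0 | 0 | 0 |

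For example, with s = 50% and p = 10%: 1 − 0.9^10 = 1 − 0.349 = 0.651.

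**The case against.** The strongest reply has five parts.

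1. *The SAP follows the protocol.* This stands. A reader might infer that the SAP departed from the protocol by collapsing the grade, but Protocol 11.4.2.5 already specifies normal/abnormal, and the SAP adds shift tables to it. The mismatch is between Protocol 9.1 and the analysis text of both documents.

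2. *Worsening is reported elsewhere.* Largely right. Findings that meet the adverse event definition are summarised by system organ class, preferred term, worst severity and age cohort. Spleen and liver volumes are analysed as change from baseline, and liver function has its own shift tables. A reader might infer that the primary safety analysis cannot show deterioration or is biased towards a favourable picture; the documents do not support that. The cover has limits. MRI is planned at screening and Weeks 26 and 52, whereas complete examinations also take place at Weeks 12 and 38. MRI volume has no bearing on the neurological examination. SAP 2.6.1.1 counts as treatment-emergent only events that started on treatment, whereas Protocol 11.4.2.1 also includes those that worsened.

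3. *The SAP plans tables by body system.* Possibly. Section 2.6.2 lists separate systems and speaks of tables in the plural, while 2.6.3 uses the singular. Under that reading, systems normal at baseline can show worsening and the ceiling concerns mainly the abdomen. The text does not settle the matter.

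4. *The grade may not be in the database by body system.* Fair. Protocol 9.1 is a general sentence on safety findings, and SAP 2.6.2 describes collection as normal versus abnormal. The case report form is not available to check.

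5. *Listings already allow individual review in about 20 patients.* Partly. SAP section 2 promises listings of the data used in tables, but a table built on two levels does not guarantee that the three-level grade is listed.

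**Conclusion.** The point holds as a defect of the examination tables. Protocol 9.1 requires three grades for components of the primary safety endpoint, and the planned analysis discards the distinction between NCS and CS. A system abnormal at baseline then has no worsening cell. Whether this affects mainly the abdomen or the whole physical examination depends on a choice that SAP 2.6.2 leaves open.

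The gain from restoring the third level lies between nothing and nearly everything, according to the unknown share graded CS at entry: for true rates of 10 to 20%, 88 to 99% with none at CS, 65 to 89% with half, and 0% with all, against 0% in the two-level table. These figures assume 20 patients, all abnormal at baseline, moving independently. They describe what a table can display. They are not the power of a test, since none is planned on the examinations and none is needed.

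Two further readings go too far. A reader might infer that I 04 makes the abdominal examination abnormal by definition; it fixes an MRI volume and says nothing about the examination grade. A reader might also infer that a three-level table cures the ceiling; it does so only for patients who start at NCS.

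The analysis is descriptive and other outputs cover part of the ground, so the consequence is limited. The change is still worth making, because it lets these tables register deterioration at little cost.

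**What to change.** In SAP 2.6.2 and 2.6.3:

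- Build the shift tables by body system on normal, abnormal NCS and abnormal CS, from baseline to each scheduled visit and to the worst on-treatment grade.
- Add a count and a listing, by age cohort and overall, of patients with new or worsened CS findings, including patients already NCS or CS at baseline. This covers those who start at CS, for whom no shift table on this scale can show worsening.

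Reconcile Protocol 9.1 with 11.4.2.5, or declare the three-level analysis as a modification in SAP 1.5.

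The cost is a change of SAP wording and a 3 × 3 table in place of a 2 × 2, with sparser cells in small cohorts. No new assessment is needed provided the case report form captured NCS and CS by body system, which should be checked first. If it did not, use the overall grade where it exists, together with examination findings linked to adverse events, and state that collection differed from Protocol 9.1.
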